7.2. Statistical Analysis Plan

7.2.1 Statistical Plan

This is an open-label phase II study aimed at establishing the efficacy of single agent pembrolizumab, at the FDA-approved dose of 200mg every 3 weeks, in patients with solid

tumors and LMD. The primary endpoint will be CNS response at 12 weeks/after 4 cycles of therapy. The sample size is calculated with Clopper-Pearson's exact binomial confidence interval method. With 16 analyzable patients, defined as eligible patients who receive at least one dose of pembrolizumab, we determine that we will have an appropriate level of estimation accuracy for the first study of this experimental regimen. The following table summarizes the two-sided 90% exact confidence interval for different observed CNS response rate. Guarding against a 10% rate of patients either being ineligible or dropping out, the final sample size is 18 patients. If a higher rate of ineligible and drop-out rate is observed during the study conduct, the protocol may be amended to ensure at least 16 analyzable cases.

No. of patients with CNS response (%)	90% Confidence Interval for Observed CNS Response Rate (N=16)	
	Lower (%)	Upper (%)
1 (6.3%)	0.3	26.4
2 (12.5%)	2.3	34.4
3 (18.8%)	5.3	41.7
4 (25%)	9.0	48.4
5 (31.3%)	13.2	54.8
6 (37.5%)	17.8	60.1

Secondary endpoints will include CNS-PFS, OS and safety. Kaplan-Meier curves will be used to assess CNS-PFS and OS. Cause of death will be recorded. Safety will be assessed as detailed above, and monitored as per JHH SKCCC Data Safety and Monitoring Plan. Exploratory endpoints will include genomic testing of tumor cells and cell-free DNA in CSF and serum, and immunologic studies of immune cells in CSF and serum at pre-defined timepoints. These data will be presented descriptively. Genomic and immunologic correlates from available tissue in selected patients, will be presented descriptively. Means and standard deviations of all markers will be computed and 95% confidence intervals will be constructed. For serum markers, linear regression model (with proper transformation of the data) will be used to compare slopes in repeated measures between pre-defined time-points. Our institution sees 250 new patients per year with advanced lung cancer, 5% of which will have LMD (n=18 in 18 months), 200 new patients with breast cancer, 5% of which will have LMD (n=15 patients in 18 months), and selected patients with other solid tumors per year with LMD (n=10 per year), not including patients in follow-up. Taking into account that this may be a less fit patient population, we conservatively estimate that we will accrue 1 patient per month at our institution and 1 additional site that have agreed to participate in the study. Study duration will be approximately 24 months, allowing 18 months for accrual and 6 months for follow-up and data analysis.

7.2.2 Responsibility for Analyses

The statistical analysis of the data obtained from this study will be the responsibility of the institution, which is the study sponsor of this trial.

This trial is being conducted as an open-label study, i.e., subjects, investigators, and sponsor personnel will be aware of subject treatment assignments after each subject is enrolled and treatment is assigned.

The Clinical Biostatistics department of the sponsor will generate the allocation schedule.

7.2.3 Hypotheses/Estimation

Objectives and hypotheses of the study are stated in Section 3.0.

7.2.4 Primary Efficacy Endpoint

CNS response

CNS response rate is defined as the proportion of the subjects in the analysis population who have a radiologic reduction in size of measurable CNS tumor lesions on an MRI brain scan, develop clearance of positive CSF cytology on 2 consecutive CSF specimens after an initial positive specimen has been obtained, or an improvement in neurologic function, as detailed in Table 8. In patients with more than one available response criterion, the most easily assessable criterion will be used.

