2.0 TRIAL DESIGN

2.1 Trial Design

This is an open-label phase II study of pembrolizumab in patients with advanced solid tumors with leptomeningeal carcinomatosis (LMD). Patients may have received any number of prior therapies for their respective solid tumors, but must not have received prior anti-PD-1 therapy and developed progressive disease. Approximately 18 subjects in this study will receive pembrolizumab at a dose of 200mg intravenously (IV) every 3 weeks (Q3W) for 4 doses. In patients who derive clinical benefit from therapy, pembrolizumab may be continued until documented disease progression, unacceptable adverse event(s), intercurrent illness that prevents further administration of treatment, investigator's decision to withdraw the subject, subject withdrawal of consent, noncompliance with trial treatment or procedure requirements, or for administrative reasons.

This study aims to determine if pembrolizumab can cause a radiologic, cytologic or clinical response in the CNS in patients with advanced solid tumors with LMD. The primary endpoint is thus central nervous system (CNS) response, defined either as radiologic response (reduction in size of LMD on gadolinium-enhanced MRI imaging of the brain and total spine including T1- weighted, T2-weighted, fluid attenuated inversion recovery and post-gadolinium sequences)

and/or cytologic response (conversion of positive to negative CSF cytology on 2 consecutive samples) and/or clinical response (Table 8), as detailed in the section 4.1.5.1.1 and 6.1.2.7.

Secondary endpoints will include progression-free survival (PFS), overall survival (OS), and safety.

Patients will undergo routine screening investigations including CBC, CMP, urine, pregnancy test, standard radiologic imaging of the body (CT), cerebrospinal fluid (CSF) sampling for cytology, and a pre-treatment gadolinium-enhanced MRI scan of the brain and total-spine. During the trial, patients will be monitored with a clinical visit, adverse event assessment and routine laboratory tests at the time of each dose of pembrolizumab. Patients will have a CSF sample taken, blood draws, radiologic imaging of the body (CT), and a contrast-enhanced MRI scan of the brain and total-spine after 2 and 4 cycles of therapy for response assessment and correlative studies. In patients with a CSF sample that demonstrates negative cytology, an additional confirmatory CSF sample will be obtained 3 weeks after the first negative CSF cytology sample.

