4.1.5.1 Efficacy Endpoints

4.1.5.1.1 Primary Endpoint:

The primary efficacy endpoint is to evaluate CNS response with pembrolizumab in patients with LMD from solid tumors. CNS response will be defined either as radiologic response, cytologic response, or clinical response, whichever is easier to assess. Radiologic response will be defined as a reduction in size of a measurable lesion on a contrast-enhanced MRI scan of the brain. Cytologic response will be defined as a negative CSF cytology result in 2 consecutive samples, in patients who have initial positive cytology prior to treatment, or a clinical response, defined as an improvement in objective neurologic signs or symptoms attributable to LMD (Table 8). Response assessment is detailed in section 6.1.2.7.

4.1.5.1.2 Secondary Endpoints:

- **1. CNS Progression-free Survival:** A secondary endpoint of this study is to evaluate CNS-PFS, which will be defined as the time from study enrollment until CNS progression (radiologic, cytologic or clinical), or death, whichever occurs first. CNS progression will be classified as radiologic (determined by contrast-enhanced MRI scan), cytologic (determined by pathologic assessment of CSF cytology including cell count, differential, glucose) or clinical progression (defined as new objective neurologic signs or symptoms, attributable to LMD), as detailed in section 6.1.2.7.
- 2. **Overall Survival:** A secondary endpoint of this study is to evaluate OS, which will be defined as the time from study enrollment until death from any cause. Deaths from progressive disease will be stratified as related to CNS progression, related to systemic progression, or both.

8A

3. **Safety:** Safety will be evaluated according to the National Cancer Institute Common Terminology Criteria for Adverse Events (NCI CTCAE) version 4.0^{27} safety will be determined by the number of treatment-related toxicities of > grade 3 severity by CTCAE Version 4.0.

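### CNS response, the primary endpoint, is defined inconsistently: the MRI threshold, the Table 8 categories that count as response and the criterion that decides are not settled

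*Combined protocol and SAP*

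**What the plan says.** **MRI.** Section 7.2.4 counts patients who "have a radiologic reduction in size of measurable CNS tumor lesions on an MRI brain scan". Section 4.1.5.1.1 reads: "Radiologic response will be defined as a reduction in size of a measurable lesion on a contrast-enhanced MRI scan of the brain". Section 2.1 speaks of "reduction in size of LMD on gadolinium-enhanced MRI imaging of the brain and total spine" and repeats the idea for a measurable lesion anywhere in the neuro-axis. The only number attached in these sections is the 3 mm cut-off for measurability; none sets a minimum reduction. Section 6.1.2.7 defines Improved by neurologic improvement and/or CSF and MRI findings, the MRI finding being 50% bidirectional shrinkage. Its definition of Stable includes a reduction in the size of LMD without progression, and gives that reduction no percentage.

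**Cross-references.** Section 2.1 defines the endpoint "as detailed in the section 4.1.5.1.1 and 6.1.2.7". Section 4.1.5.1.1 adds: "Response assessment is detailed in section 6.1.2.7". Section 7.2.4 points to Table 8, which contains no percentages.

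**CSF.** Section 7.2.4 requires that patients "develop clearance of positive CSF cytology on 2 consecutive CSF specimens after an initial positive specimen has been obtained"; 2.1 and 4.1.5.1.1 give the same two-sample rule. Section 6.1.2.7 also admits a 50% fall in CSF tumor cells to Improved.

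**Deciding criterion.** Section 7.2.4: "In patients with more than one available response criterion, the most easily assessable criterion will be used". Section 4.1.5.1.1: "CNS response will be defined either as radiologic response, cytologic response, or clinical response, whichever is easier to assess". Section 2.1 instead joins the three kinds of response with and/or, and Table 8 combines neurologic function with MRI or CSF into one overall category.

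**Reporting.** Table 12 plans the response proportion with a 95% exact confidence interval and no formal inference.

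**The concern.** The trial is open-label and single-arm, and its main efficacy result is one proportion. If the rule for counting a responder is not fixed, neither is the numerator. The choice of MRI threshold, of qualifying Table 8 categories and of deciding criterion could then be made with the outcomes known. Section 4.1.4.4 describes this very difficulty in the LMD literature: response was defined in different ways, so historical rates are hard to interpret. A rate from this trial would have the same weakness.

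**Working it through.** **1. The plan's own figures.** Section 7.2.1 wants 16 analyzable patients and allows 10% for ineligibility or dropout: 16/0.9 = 17.8, rounded up to 18. This reproduces. Its intervals are Clopper-Pearson, two-sided 90%, N=16. For x responders among n, with α = 0.10, the lower limit is the α/2 quantile of Beta(x, n−x+1) and the upper limit is the 1−α/2 quantile of Beta(x+1, n−x). This gives 2.3-34.4 for 2/16 and 9.0-48.4 for 4/16, as printed. Eleven of the twelve printed limits reproduce. The exception is the upper limit for 6/16, printed 60.1 and computed 60.9, which has no bearing here.

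**2. The rules applied to hypothetical patients.**

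| Patient | 7.2.4 as worded | 6.1.2.7 / Table 8 |
|---|---|---|
| MRI shrinkage of 30%, nothing else changed | Responder | Not Improved by MRI |
| CSF tumor cells down 50%, cytology still positive | Not a responder | Improved on cell count; persistent positive cytology is listed under both Improved and Progression |
| Positive at baseline, then two consecutive abnormal reads | Responder, if abnormal means negative as 6.1.2.7 first defines it | Stable, where 6.1.2.7 lists the abnormal read again |
| Neurologic function improved, MRI progressing | Responder if any one criterion suffices; otherwise depends on which criterion is judged easiest | Progression |
| MRI improved, neurologic function progressing | As above | Progression |

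The first row is the MRI conflict. The second matters if Improved counts as response, which no section states or denies. The third comes from within 6.1.2.7, so giving that section precedence would not settle it. The last two show the selection clause against Table 8.

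**3. Size.** One patient is 1/16 = 6.25 points, or 1/18 = 5.6 points if all 18 are analyzable. The shift can go either way: an unlimited size reduction adds responders, while Table 8's combination, or an easiest criterion that happens not to be met, removes them.

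The documents give no distribution of shrinkage or of discordance, so the counts below are assumed: two patients are responders under every reading and two more under only some. The intervals are 95% Clopper-Pearson (α = 0.05 in the formula above), the level that Table 12 names for reporting.

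- N=16: 2/16 = 12.5% (1.6-38.3) against 4/16 = 25.0% (7.3-52.4).
- With one or three disputed patients instead: 3/16 = 18.8% (4.0-45.6) or 5/16 = 31.3% (11.0-58.7).
- N=18: 2/18 = 11.1% (1.4-34.7) against 4/18 = 22.2% (6.4-47.6).

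**The case against.** The best defence is that 2.1, 4.1.5.1.1 and 7.2.4 are summaries and 6.1.2.7 is the operational section to which they lead. That is a fair reading, and the 50% criterion may be what was intended. It does not close the matter: the referring sections state an MRI rule of their own, Table 8 carries no threshold, nothing gives precedence, and 6.1.2.7 is itself inconsistent on cytology.

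A reader might infer three stronger points that the documents do not support.

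- That 6.1.2.7 expressly calls shrinkage below 50% stable, or requires 50% shrinkage for Improved. In the Stable definition the percentage is attached to CSF tumor cells, and the size-reduction clause has none. Neurologic improvement alone can also qualify as Improved.
- That the cytologic rule for the primary endpoint differs between sections. The two-negative rule is the same in 2.1, 4.1.5.1.1 and 7.2.4. The 50% cell decrease defines a category, and it becomes a competing rule only if that category counts as response.
- That nobody is assigned to judge response, or that a choice after the data are seen is planned. Section 6.1.2.7.1 has the site team confirm at screening that the patient is assessable, 2.1 gives clinical response to the treating investigator, and 2.1 requires independent confirmation of imaging. These are real safeguards. They do not say who ranks ease among several available criteria, by what rule or when, so a late choice is possible but not planned.

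Two smaller points should not be pressed. The lack of a Table 8 row for improvement on both sides may be a loss in text extraction. The brain-only MRI wording in 4.1.5.1.1 and 7.2.4 is loose drafting, since spine MRI is scheduled.

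It is also true that there is no null rate or decision threshold, and that the illustrative intervals overlap widely. This limits the consequence to the estimate, but the estimate is the result.

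**Conclusion.** The concern holds and should be fixed before analysis. Three things are unsettled: the MRI threshold, the mapping from Table 8 categories to CNS response (together with the cytology contradictions inside 6.1.2.7), and the criterion that decides when several are available. The exact effect is 6.25 points per patient classified differently at N=16, or 5.6 at N=18, in either direction. The change from 12.5% to 25.0% rests on an assumed two disputed patients; how many there would be cannot be learned from the documents. No error rate or sample size is affected, because the plan makes no formal test and sizes on interval precision alone. What suffers is the meaning of the reported proportion and its interval.

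**What to change.** Before analysis, by wording alone:

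1. Put one definition of CNS response in 7.2.4, at the time point given in 7.1 and 7.2.1 (12 weeks/after 4 cycles), which 7.2.4 now omits. State which Table 8 categories count, and make 2.1, 4.1.5.1.1 and 6.1.2.7 refer to it.
2. Pre-specify one MRI threshold for leptomeningeal lesions on brain or spine MRI. The only shrinkage threshold in the protocol is the 50% bidirectional criterion. Report the responder count under the other threshold as a sensitivity analysis.
3. State that cytologic response for the primary endpoint is negative cytology on two consecutive samples, and code an abnormal read one way throughout.
4. Delete the ease-of-assessment clauses in 7.2.4 and 4.1.5.1.1. Replace them with a fixed rule for combining assessable criteria, including discordant ones. One example is at least one criterion met and none showing progression. It is usable only once Progression no longer overlaps with Improved; as 6.1.2.7 stands, a patient with clear MRI shrinkage and still-positive CSF could fail it.
5. The sponsor must reconcile the overlapping Improved, Stable and Progression wording in 6.1.2.7, Table 8 and the discontinuation criterion in 4.9 that relies on it. No position is taken here on which is right.

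The cost is a protocol and SAP text change, with no new assessments and no change in sample size. The response rate may look less favourable if the 50% threshold is adopted.

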After completion of 4 cycles of therapy, subjects will be evaluated every 6-9 weeks with radiologic imaging of the body (CT) and CNS (MRI) to assess response to treatment both inside and outside of the CNS. Response assessments will be completed by a radiologist at the treating site, findings will be confirmed by an independent radiologist, and evaluated by RECIST 1.1 criteria and immune-related criteria (irRC) for systemic disease, and MRI criteria for CNS disease. Following the first radiologic assessment of the body that demonstrates radiologic progressive disease (PD), RECIST 1.1 will be adapted as described in section 6.1.2.7.5 (Table 9) to accommodate for the tumor response patterns seen with pembrolizumab treatment (e.g., tumor flare) using immune-related RECIST criteria. Contrast-enhanced MRI Brain scans will be used to assess for measurable disease in the CNS at the time of screening, and to determine CNS radiologic response during the study. CNS radiologic response by MRI will be defined as a reduction in size of a measurable lesion throughout the neuro-axis, where a measurable lesion will be defined as one that is greater than or equal to 3mm in size, as detailed in section 6.1.2.7. CNS cytologic response will be assessed by two serial CSF cytology samples, as detailed in the section 6.1.2.8.3. Clinical response will be evaluated by the treating investigator, detailed in section 6.1.2.7 (Table 8).

[figure not shown]
After completion of 4 cycles of therapy or the patient's last dose of therapy, each subject will be followed for 90 days after the end of treatment for adverse event monitoring, or 30 days after the end of treatment if the subject initiates new anti-cancer therapy. Subjects who discontinue treatment for reasons other than PD will have post-treatment follow-up for disease status until PD, initiation of a new cancer therapy, withdrawal of consent, or becoming lost to follow-up. All subjects will be followed by telephone contact for overall survival (OS) until death, withdrawal of consent or the Investigator is notified by the Sponsor to discontinue follow-up, whichever comes first.

This trial will be conducted in conformance with Good Clinical Practices.

Specific procedures to be performed during the trial, as well as their prescribed times and associated visit windows, are outlined in the Trial Flow Chart – Section 5.0 Details of each procedure are provided in Trial Procedures- Section 6.0.

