A limited number of prospective studies have been completed in patients with solid tumors and LMD. Most recently a phase II study of single agent temozolamide demonstrated a

needed

response rate of 15.8% $(n=3/19)^{55}$, and single agent pemetrexed, 4% (n=1/21), in all solid tumors⁵⁶ (Table 1).

Patients with areas of bulky LMD that cause obstruction of CSF flow or are thought to be causing neurologic deficit, may be treated with local radiation therapy (RT) or WBRT for palliation (Figure 1). There are no prospective clinical studies evaluating the use of local RT or WBRT alone, however the Southwest Oncology Group (SWOG) investigated the combination of WBRT and IT-MTX in solid tumors in 1988⁵⁷ (Table 1).

Interpretation of clinical studies in patients with LMD are complicated by a lack of randomized data, and a variety of response assessments used in reported studies. In the studies detailed in Table 1 below, response may have been captured as clinical response, radiologic response, or cytologic response, or a combination of two or three of these response assessments, defined in different ways. Definitions for clinical response on these studies included: improvement or stability in neurologic symptoms^{34,58}, improvement in neurologic function and KPS at 1 month³⁵, or improvement in neurologic function with cessation of steroid use⁵⁵. Definitions for radiologic response in these studies included: reduction in size of measurable lesions on brain MRI^{36,55}, CT brain or myelogram³¹; and definitions for cytologic response may have referred to clearance of previously positive CSF cytology at 1 month³⁵, or on 2 or more consecutive CSF samples³⁴. In one study, response was defined by clinical, radiologic and cytologic parameters, such that a complete responder would demonstrate a normal neurologic examination, negative CSF cytology, normal CSF protein and glucose, and no measurable disease on CT or myelogram³¹. In a second study, response was defined by clinical and cytologic parameters, with the combination of a negative CSF cytology assessment and stable/improved neurologic function as response³². Additionally, selected studies included patients with both LMD and parenchymal brain metastases, which may confound the interpretation of some response data^{36,56}. Therefore, historical data of response rates in patients with LMD are subject to wide variability and interpretation.

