4.2.7 Subject Exclusion Criteria

The subject must be excluded from participating in the trial if the subject:

- 1. Is currently participating and receiving study therapy or has participated in a study of an investigational agent and received study therapy or used an investigational device within 4 weeks or 5 half-lives of the first dose of treatment, whichever is shorter.
- 2. Has a diagnosis of immunodeficiency or is receiving systemic steroid therapy that exceeds a maximum amount of 10mg of prednisone/day or any other form of immunosuppressive therapy within 7 days prior to the first dose of trial treatment.
- 3. Has a known history of active TB (Bacillus Tuberculosis)
- 4. Hypersensitivity to pembrolizumab or any of its excipients.
- 5. Has had a prior anti-cancer monoclonal antibody (mAb) within 4 weeks prior to study Day 1 or who has not recovered (i.e., ≤ Grade 1 or at baseline) from adverse events due to agents administered more than 4 weeks earlier.
- 6. Has had prior chemotherapy, targeted small molecule therapy other than pre-specified allowed agents detailed in section 4.2.6, or who has not recovered (i.e., ≤ Grade 1 or at baseline) from adverse events due to a previously administered agent.
 - Note: Subjects with ≤ Grade 2 neuropathy are an exception to this criterion and may qualify for the study.
 - Note: If subject received major surgery, they must have recovered adequately from the toxicity and/or complications from the intervention prior to starting therapy.
- 7. All major surgery including prior surgery to the brain within 3 weeks of commencement of study therapy.
- 8. Has a known additional malignancy that is progressing or requires active treatment. Exceptions include basal cell carcinoma of the skin or squamous cell carcinoma of the skin that has undergone potentially curative therapy or in situ cervical cancer.

- 9. Subjects with previously treated brain metastases may participate provided they are not using escalating steroids for brain metastases at the time of trial consent and study drug initiation, and there remains a measurable lesion in the CNS, as per section 4.2.6.

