6.1.2.7 Tumor Imaging and Assessment of Response

Evaluation of response will include an evaluation of neurologic signs and symptoms (normal, improved, stable, deteriorated), CSF obtained from a previous positive site (lumbar or ventricular), and repeated radiologic evaluation of all ancillary studies (MRI Brain and Total spine with gadolinium contrast enhancement and CT scans of the body). Patients will be evaluated for CNS response based on a 4-point scale: complete response, improvement, stable disease and progression, as detailed in the Table below:

Table 8: Determination of Response to LMD

Clinical Assessment (Neurologic Function)	Size of LMD disease on MRI or CSF cytology	Overall Response Determination
No neurologic symptoms	None detectable	Complete response

Improved	Stable	Improved
Stable	Improved	Improved
Stable	Stable	Stable
Improved	Progression	Progression
Stable	Progression	Progression
Progression	Improved or Stable	Progression

We will define a positive CSF cytology result either detectable malignant cells in the CSF, or a pathology read that is reported as "suspicious for malignancy." We will define a negative CSF cytology result as either no detectable malignant cells in CSF, or a pathology read of "abnormal CSF cytology response," which will indicate conversion from positive/suspicious to negative/abnormal CSF cytology^{31,32}.

A complete responder will be defined as a patient with a normal neurologic examination, negative CSF cytology and no measurable leptomeningeal masses on radiologic imaging. Improved patients will be defined as those that have demonstrated improvement in neurologic signs or symptoms and/or a 50% decrease in CSF tumor cells or persistent positive CSF cytology as defined above, a 50% shrinkage in the bidirectional measurements of leptomeningeal disease. Patients with stable disease will be defined as less than 50% improvement in number of CSF tumor cells or abnormal CSF cytology response as defined above, or reduction in size of LMD on radiologic assessment, without evidence of progression. Progression will be defined as more than 25% increase in the number of tumor cells or persistent positive CSF cytology as defined above, an increase in size of LMD masses on radiologic assessment, or the development of new neurologic signs or symptoms after at least 2 cycles of pembrolizumab therapy.

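### The primary endpoint defines radiologic response in two incompatible ways: any measurable CNS lesion on brain MRI, or leptomeningeal disease on brain and total-spine MRI

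*Combined protocol and SAP*

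**What the plan says.** Five places in the combined protocol and SAP describe the radiologic limb of CNS response.

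- **Section 7.2.4**, from which the primary rate is calculated: "radiologic reduction in size of measurable CNS tumor lesions on an MRI brain scan".
- **Section 4.1.5.1.1**: "Radiologic response will be defined as a reduction in size of a measurable lesion on a contrast-enhanced MRI scan of the brain".
- **Section 2.1, endpoint paragraph**: "reduction in size of LMD on gadolinium-enhanced MRI imaging of the brain and total spine".
- **Section 2.1, later paragraph**: "CNS radiologic response by MRI will be defined as a reduction in size of a measurable lesion throughout the neuro-axis". Here measurable means at least 3 mm, and the lesion type is not stated. The same paragraph also says "Contrast-enhanced MRI Brain scans will be used to assess for measurable disease in the CNS at the time of screening" and gives those brain scans the task of determining radiologic response.
- **Section 6.1.2.7 and Table 8**: the table column is "Size of LMD disease on MRI or CSF cytology", and the text evaluates brain and total-spine MRI.

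On eligibility, inclusion 4A (section 4.2.6) accepts a measurable lesion on either brain or total-spine MRI, and 4B accepts positive CSF cytology alone. Exclusion item 9 (section 4.2.7) lets patients with previously treated brain metastases enter provided, among other things, that "there remains a measurable lesion in the CNS, as per section 4.2.6". Table 7 schedules MRI of brain and full spine at screening and at each restaging.

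**The concern.** The trial is motivated by a contrast. Sections 4.1.4.3 and 4.1.5 report that checkpoint blockade has shown activity in parenchymal brain metastases and is unstudied in LMD. If parenchymal shrinkage can count, the primary rate may partly restate the known activity as evidence in the new setting. The protocol makes this criticism of earlier work in section 4.1.4.4: "selected studies included patients with both LMD and parenchymal brain metastases, which may confound the interpretation of some response data".

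Attribution is a second problem. Inclusion item 8 allows prior whole-brain radiotherapy without a fixed washout, and the three-month radiation limit in 4A applies only to the qualifying lesion. A recently irradiated metastasis could therefore shrink on study and be counted.

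The brain-only wording errs in the other direction, because real regression of spinal LMD would not count as radiologic response. With 16 analysable patients, a few such classifications decide what the trial reports.

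**Working it through.** **1. The texts side by side**

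| Place | Lesion type | Region |
|---|---|---|
| 7.2.4 | any measurable CNS tumor lesion | brain |
| 4.1.5.1.1 | any measurable lesion | brain |
| 2.1, later paragraph | any measurable lesion, at least 3 mm | neuro-axis, but brain MRI named as the tool |
| 2.1, endpoint paragraph | LMD | brain and total spine |
| 6.1.2.7 / Table 8 | LMD | brain and total spine |

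The cross-references do not resolve this. In 7.2.4 the pointer to Table 8 follows the neurologic-function limb. In 4.1.5.1.1 Table 8 is attached to clinical response, and the general pointer to 6.1.2.7 only sets a second definition beside the first. Section 7.2.4 also says that, where several criteria are available, the most easily assessable one is used. One brain-lesion measurement could then decide a patient's status.

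**2. The plan's own figures (section 7.2.1)**

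Sample size: 16 / (1 − 0.10) = 17.8, rounded up to 18, as stated. The 90% Clopper-Pearson table at N=16 reproduces in 11 of its 12 limits. The exception is the upper limit for 6/16, printed as 60.1 and computed as 60.9, which has no bearing here. One patient is 1/16 = 6.25 points: for example, 3/16 = 18.8% (90% CI 5.3 to 41.7) against 4/16 = 25.0% (9.0 to 48.4).

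**3. Possible inflation from parenchymal lesions**

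Inputs:
- b, share of patients with a measurable parenchymal lesion: 0.20 to 0.50. This is an assumption; the documents give no figure.
- q, parenchymal response: 0.25 to 0.50, from section 4.1.4.3 (3 responders among 12 evaluable melanoma patients; 5/10 in NSCLC).
- p, true LMD response: 0.10 to 0.20 (assumption).
- Parenchymal and LMD response independent (assumption).

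Apparent rate = p + (1 − p) × b × q, so inflation = (1 − p) × b × q.

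- Smallest: (1 − 0.20) × 0.20 × 0.25 = 0.040, or 4 points (16 × 0.040 = 0.64 patients).
- Largest: (1 − 0.10) × 0.50 × 0.50 = 0.225, or 22.5 points (16 × 0.225 = 3.6 patients).

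**4. Possible loss from spine-only LMD**

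If a share s of radiologic responders has spine-only disease and only brain MRI counts, the recorded radiologic rate is p × (1 − s). Take a true radiologic rate of 20% and s = 0.10 to 0.50 (both assumptions). The recorded rate is then 0.20 × 0.90 = 18% down to 0.20 × 0.50 = 10%. This concerns the radiologic limb alone. Some of these patients would be recovered through the clinical or cytologic limb.

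**The case against.** The strongest reply is that the intended meaning is already LMD. Inclusion 4 uses the measurable lesion to define radiologically detectable LMD. Section 6.1.2.7.2 introduces the 3 mm cut-off because no LMD criteria exist. Exclusion item 9 refers back to section 4.2.6. Sections 2.1 and 4.1.5.1.1 send the reader to 6.1.2.7, and 7.2.4 cites Table 8. This shows what was probably meant, and it means the any-lesion rule cannot be called the plan's settled position. It does not remove the contradiction, because the section that defines the analysed proportion says something else.

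Four stronger readings are tempting and are not supported:

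- *Spine-only LMD cannot be scored at all.* It can be, by clinical improvement, by cytologic clearance if CSF was positive at baseline, and radiologically under 2.1 or 6.1.2.7. Only the radiologic route under 7.2.4 and 4.1.5.1.1 is closed.
- *Section 7.2.4 contradicts objective 3.1.* That objective speaks of a response in the CNS in patients with LMD, which a brain-lesion response literally satisfies. The conflict is with 2.1 and 6.1.2.7.
- *A patient with a shrinking metastasis and persistently positive CSF is plainly a responder.* Section 6.1.2.7 mentions persistent positive cytology under both improvement and progression, so that patient's status is also unsettled.
- *The inflation is 5 to 25 points.* That is b × q without removing patients who would respond anyway. It is an upper bound on the same inputs.

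It is also fair to say that the response rates in section 4.1.4.3 come from metastases not needing immediate local therapy, whereas item 9 concerns previously treated ones, so they may not transfer. Positive correlation between the two kinds of response would lower the figure further. In the other direction, 7.2.4 accepts any reduction in size, which is easier to meet than a partial response.

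**Conclusion.** Wrong as written. The radiologic limb of the primary endpoint has incompatible definitions, and the same scans could give different primary rates depending on the section followed. Under 7.2.4, parenchymal shrinkage can count and spine-only LMD has no radiologic route.

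The inflation of about 4 to 22.5 points is illustrative. It rests on an assumed share of patients with parenchymal lesions, response rates borrowed from a different brain-metastasis population, an assumed true LMD response of 10-20%, and independence. The 6.25 points per reclassified patient needs none of these except N=16.

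The plan is estimation only, with no null rate or decision threshold, so no error rate or power is affected. What is affected is the meaning of the one rate the trial was set up to estimate.

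**What to change.** Use one definition of radiologic response in both paragraphs of section 2.1 and in sections 4.1.5.1.1, 6.1.2.7 (with Table 8) and 7.2.4: reduction of measurable leptomeningeal lesions anywhere on the brain and total-spine MRI. Have the site radiologist and the independent radiologist, both already planned in section 2.1, label each baseline lesion as leptomeningeal or parenchymal. Report parenchymal response separately and do not count it toward the primary endpoint.

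The degree of shrinkage also differs between sections (any reduction in 4.1.5.1.1 and 7.2.4, 50% in 6.1.2.7). That is a separate point, but it should be settled in the same edit.

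The cost is wording in these sections and one extra field on the imaging case report form. No scans or readers are added, and the sample size stays at 18 enrolled for 16 analysable. The reported response rate may be lower.
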